2.1.2 Secondary Objectives

- To assess changes in absolute PASI scores from baseline to Week 16
- To assess the mean percent change in PASI scores from baseline to Week 16
- To assess safety and tolerability of KD025
- To assess changes in Physicians Global Assessment (PGA)
- To assess changes in Dermatology Life Quality Index (DLQI)
- To assess changes in PASI scores from baseline to Week 48 for subjects receiving 48 weeks of KD025 treatment

- To evaluate the difference in PASI scores between Week 16 and Week 48 for subjects receiving KD025 for a total of 48 weeks

2.1.3 Exploratory Objectives

To evaluate the concentration and changes in IL-17 expression in blood, tissue before and after 16 weeks of dosing with KD025

2.2 Study Design

This is a Phase 2, double blind, randomized, placebo-controlled, dose-finding, safety, tolerability, and efficacy study.

This study will be performed in adult male and female subjects with moderate to severe chronic plaque psoriasis who are candidates for systemic therapy or phototherapy. Subjects who have signed an Institutional Review Boards/Independent Ethics Committees (IRBs/IECs) approved informed consent form (ICF) and have met all of the inclusion/exclusion criteria will be enrolled. Approximately 110 subjects will be randomly assigned to each of the 5 dose cohorts in a 1:1:1:1:1 manner to achieve 22 evaluable subjects at 16 weeks in each cohort.

Table 1: Cohorts

Cohort	Number of Subjects	Treatment
Cohort 1	~22	200 mg KD025 QD
Cohort 2	~22	200 mg KD025 BID
Cohort 3	~22	400 mg KD025 QD
Cohort 4	~22	600 mg/day KD025 (administered as 400 mg in the morning and 200 mg in the evening)
Cohort 5	~22	Matching placebo BID

Study drug will be orally administered in a double-blind fashion for an initial 16 weeks. All subjects will be given the option to receive KD025 400 mg QD for an additional 32-weeks in an open-label treatment period (week 16 through week 48).

For all subjects, including those who discontinue from the study prematurely, a Follow-Up visit will occur 30 days (\pm 3 days) after the last dose of study drug.

2.3 Visit Schedule and Study Assessment

The flow chart of visit schedule and study assessments is given in study protocol Table 1.

3 STATISTICAL METHODS

3.1 General Methods

3.1.1 Computing Environment

All statistical programming and data analyses will be performed using SAS[®] Version 9.4 on Windows platform.

3.1.2 General Considerations

General considerations for descriptive statistics and presentation for continuous and categorical data are given below.

Continuous data will be described using descriptive statistics: number of observations (n), mean, standard deviation, median, minimum and maximum. Frequencies and percentages will be used for summarizing discrete (categorical) data. When categorical data are presented, the percent will be suppressed when the count is zero in order to draw attention to the nonzero counts. The denominator for all percentages, unless otherwise specified, will be the number of subjects in the cohort or in the specified analysis population.

Means, medians, standard deviations, and confidence intervals (CI) will be reported to one decimal place more than the data reported on the CRF or by the vendor. Minimum and maximum will be reported to the same number of decimal places displayed on the CRF or by the vendor. P-values will be reported to 4 decimal places.

Efficacy analysis will be performed on blinded period and entire treatment duration. Safety analysis will be performed on blinded period, open-label period and entire treatment duration.

Unless otherwise indicated, all summary tables for blinded period and entire treatment duration will be presented by the following groups: cohort 1, cohort 2,

cohort 3, cohort 4, cohort 5, and all KD025. For open-label period, summary tables will be presented by the actual dose group (400 mg KD025 QD for all subjects).

Because of the exploratory nature of the study, no adjustments will be made for the multiplicity of endpoints.

Last Observation Carried Forward (LOCF) method will be incorporated when applicable.

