3.1.4 Baseline

Two different types of baseline are defined considering the different periods in this study.

For blinded period and entire treatment duration, baseline value is defined as the valid and last non-missing value obtained within 28 days prior to subject receiving the first study medication, unless otherwise stated under the related assessment section. Baseline can be the day before the first study medication or on the same day as the first study medication if a pre-dose assessment is available. Subjects without data on a parameter before the first study medication will have a missing baseline for this parameter.

For open-label period, baseline value is defined as the last non-missing assessment value on or before Week 16.

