3.2 Analysis Populations

Modified Intent-to-treat (mITT) Population: Modified Intent-to-treat (mITT) Population is defined as all subjects who receive at least 1 dose of study medication.

The mITT Population will be used for tables of demography, baseline characteristics and efficacy analyses.

Safety: The safety population is defined as all subjects who receive at least one dose of study medication. In this study, safety population is equivalent to mITT population.

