3.9 Safety Analysis

Safety assessments include AEs, serious adverse events (SAEs), vital sign measurements, clinical laboratory evaluations (hematology and chemistry), and ECGs. Unscheduled visits for safety assessments will not be presented in summary tables, but will be presented in listings. All safety analyses will be performed using the safety population.

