3.9.1 Adverse Events

AEs will be coded using the Medical Dictionary for Regulatory Activities (MedDRA) dictionary (Version 20.0 or higher). TEAEs for blinded period and entire treatment duration are any AEs occurring or worsening in severity after the first administration of study medication. TEAEs for open-label period are any AEs occurring or worsening in severity after Week 16. All AEs (including SAEs) will be graded using the 5-point CTCAE V5.0 scale (mild, moderate, severe, life threatening, or death); their causality with KD025 will be classified into following 5 classes: definitely related, probably related, possibly related, unlikely related, not related. The Investigator will further assess the relationship of adverse events to cGVHD or the underlying disease.

The number and percentage of patients who experienced at least one TEAE as well as the number and percentage of patients who experienced adverse events of each specific system organ class (SOC) and preferred term (PT) will be presented. For the presentation of AE incidences, the SOCs and the PTs within each SOC will be presented by decreasing total frequency. Tabulation by maximum severity and relationship to KD025 will also be included by treatment group.

TEAEs, Grade ≥ 3 TEAEs, SAEs and TEAEs leading to dose modification / discontinuation will be summarized according to treatment arm, system-organ-class, and preferred terms. These analyses will be repeated for events considered related (definitely related / probably related / possibly related) to KD025.

Subject listings will be provided for SAEs, AEs resulting in study drug discontinuation and deaths.

AEs will also be presented in listings. Time to onset and duration of AEs will be included in listings, along with action taken and outcome.

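### The SAP plans separate open-label safety tables but defines no open-label population and does not tie open-label adverse events to an open-label dose

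*SAP*

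**What the plan says.** - **Optional entry.** SAP 2.2: "All subjects will be given the option to receive KD025 400 mg QD". Protocol 9.2 confirms that this includes subjects randomised to placebo. Neither document states or assumes an uptake.
- **Separate tables.** SAP 3.1.2: "Safety analysis will be performed on blinded period, open-label period and entire treatment duration". The blinded and entire-duration tables keep cohorts 1 to 5. The open-label tables do not: "For open-label period, summary tables will be presented by the actual dose group (400 mg KD025 QD for all subjects".
- **Population.** SAP 3.2: "The safety population is defined as all subjects who receive at least one dose of study medication". It states that this equals the mITT population. SAP 3.9: "All safety analyses will be performed using the safety population". Table 4 in SAP section 4 assigns the Safety population to the AE, laboratory, vital-sign and ECG outputs. Protocol 12.3 adds only an Evaluable for Efficacy population.
- **Denominator.** SAP 3.1.2: "The denominator for all percentages, unless otherwise specified, will be the number of subjects in the cohort or in the specified analysis population".
- **Event rule.** SAP 3.9.1: "TEAEs for open-label period are any AEs occurring or worsening in severity after Week 16".
- **Collection window.** Protocol 11.2 records AEs until 30 days after the last dose, and protocol 7.1.6 schedules a follow-up visit for every subject at that point.

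**The concern.** The first dose of study medication is always a blinded one. Membership of the Safety population therefore says nothing about whether a subject took open-label KD025. Two errors follow if the rules are applied as written:

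- A subject who left before Week 16, or declined to continue, stays in the denominator of the open-label AE tables.
- A subject who stopped at Week 16 is still followed for 30 days. An event in that time meets the open-label rule and falls in the 400 mg QD column, even if the subject only ever took placebo. If causality was not recorded, SAP 3.1.5 also treats the event as related to KD025.

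The single column is a separate matter. Former placebo subjects meet KD025 for the first time at Week 16, while the other entrants have already had 16 weeks on it. Safety and tolerability of KD025 is a secondary objective, and these crossovers are the only new first exposures in the open-label period. The table would not show them separately.

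**Working it through.** The plan gives no figure for open-label size, uptake or event rate, so there is none to reproduce. The check is on what the rules produce.

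**Inputs from the documents**
- N = 110 subjects (SAP 3.12), taken as all dosed.
- Allocation 1:1:1:1:1 (SAP 2.2), so placebo is 22/110 = 20%.

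**Assumptions**
- u, the share entering the open-label period: 50%, 70%, 90%.
- r, the true AE rate among subjects given open-label drug: 20%, purely illustrative.
- q, the rate of AEs after Week 16 among non-continuers: 0% or 10%.

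**Denominator.** With the full Safety population as denominator, the displayed rate is

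u × r + (1 − u) × q.

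The understatement relative to r is (1 − u) × (1 − q/r).

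| Uptake | Entrants of 110 | Displayed, q = 0 | Understatement | Displayed, q = 10% | Understatement |
|---|---|---|---|---|---|
| 90% | 99 | 18% | 10% | 19% | 5% |
| 70% | 77 | 14% | 30% | 17% | 15% |
| 50% | 55 | 10% | 50% | 15% | 25% |

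With q = 0 the understatement is 1 − u whatever r is. If q equals r there is no net understatement, but (1 − u) of the displayed rate then comes from subjects who took no open-label drug. With an Open-Label Safety population as denominator and a dose-based event rule, the table shows 20% in every row.

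The one related planning figure is the 17% expected to lack a Week 16 PASI score (SAP 3.12). It is not an uptake assumption. Taken as a rough proxy for not entering, it gives 0.83 × 110 ≈ 91 entrants and, with q = 0, a relative understatement of 17%. Each subject who completes Week 16 and declines adds to that.

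**Share of first exposures.** If uptake is equal across cohorts, former placebo subjects are 20% of entrants, at most about 22 people. If placebo uptake is half that of the KD025 cohorts, the share is (0.2 × 0.5)/(0.2 × 0.5 + 0.8) = 0.1/0.9 ≈ 11%. If it is double, the share is 0.2/(0.2 + 0.8 × 0.5) = 0.2/0.6 ≈ 33%.

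**Do other planned tables recover the crossovers?** The entire-duration tables keep cohort 5 as its own column, but that column combines 16 weeks on placebo with later time on KD025. Setting it against the blinded table for cohort 5, and using time to onset in the AE listings, allows a partial reconstruction. No planned summary table gives the crossover rate directly.

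**The case against.** The strongest reply is that section 3.1.2 groups the open-label tables by the dose actually taken. A subject with no open-label dose has no such group, and the denominator rule allows the group size as an alternative to the population. On that reading there is no dilution and no placebo-only subject in the column. This reading is reasonable, but sections 3.2, 3.9 and 3.9.1 and the table list point to the full Safety population, and nothing settles the matter. Two programmers could produce different denominators from the same text.

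Four further points stand and limit what can be claimed:

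- Non-continuers' events offset part of the dilution, as the q = 10% columns show. A reader might infer that open-label AE rates must come out too low, but the direction depends on q.
- A reader might infer that pooling crossovers with pre-treated subjects biases the rate. It does not. The pooled figure is a correct average over everyone on open-label 400 mg QD; what is lost is the separate first-exposure rate.
- A reader might infer that laboratory percentages are diluted in the same way. SAP 3.1.5 drops subjects with missing data from categorical percentages, so the dilution concerns AE incidence.
- Section 3.1.4 says "For open-label period, baseline value is defined as the last non-missing assessment value on or before Week 16". A reader might infer that a laboratory rise already present at Week 16 in cohorts 1 to 4 disappears from view. The entire-duration shift tables still show it, because there the baseline precedes the first study medication.

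These are also descriptive tables in a Phase 2 study that ended early, and the primary comparison is untouched.

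**Conclusion.** The point holds as a conflict between the SAP's own rules. The population and event definitions, applied as written, give a wrong denominator and can place events in subjects without open-label drug under KD025 400 mg QD. The wording of the column suggests otherwise. The documents do not support saying that the tables will certainly be diluted.

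The size depends on uptake, which is not given. On the literal reading, AE incidence is understated by 10% to 50% in relative terms for uptake of 90% down to 50% if non-continuers contribute no events. With the illustrative rates of 10% and 20%, the range is 5% to 25%.

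The loss of the first-exposure information holds under either reading and concerns about one entrant in five with equal uptake. The open-label AE rates cannot be interpreted safely until the rules are aligned, so the SAP should be changed, although no efficacy conclusion rests on it.

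**What to change.** - **SAP 3.2:** define an Open-Label Safety population as subjects who take at least one dose of open-label KD025. Use its size as the denominator of the open-label AE tables, and amend 3.9 and Table 4 to match.
- **SAP 3.9.1:** define open-label TEAEs as AEs that start or worsen on or after the first open-label dose in that population. Keep the post-Week-16 events of non-continuers with their blinded arm. The blinded-period rule has no closing date, so these events already meet it; the edit takes them out of the open-label tables.
- **SAP 3.1.2:** show the open-label tables in three columns: placebo to KD025, KD025 to KD025, and total.

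No additional laboratory shift table is needed. The cost is SAP wording, one population flag and two extra columns, with no new data. The downside is that the placebo-to-KD025 column holds at most about 22 subjects, so its percentages will be imprecise.

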3.1.3 Study Day

The study day for all assessments prior to the first study drug administration is calculated as the difference between the date of the event or measurement (e.g., AE onset date, assessment date, sample collection date, etc.) and the start date of study treatment. The day before the start of study treatment is Study Day -1.

The study day for all post assessments after the first study drug administration is calculated as the difference between the date of the event or measurement (e.g., AE onset date, assessment date, sample collection date, etc.) and the start date of study treatment, plus one day. The first day of study treatment is Study Day 1.

3.1.4 Baseline

Two different types of baseline are defined considering the different periods in this study.

For blinded period and entire treatment duration, baseline value is defined as the valid and last non-missing value obtained within 28 days prior to subject receiving the first study medication, unless otherwise stated under the related assessment section. Baseline can be the day before the first study medication or on the same day as the first study medication if a pre-dose assessment is available. Subjects without data on a parameter before the first study medication will have a missing baseline for this parameter.

For open-label period, baseline value is defined as the last non-missing assessment value on or before Week 16.

3.1.5 Handling of Incomplete or Missing Data

Missing data will not be imputed in general and will be reported as missing in all listings. For categorical variables, patients with missing data are not included in calculations of percentages unless otherwise specified.

Missing start and end dates for AE and concomitant medication (CM).

The assumption will be the worst or most conservative judgment when imputing AE and CM start and end dates. The purpose of imputing a start date is to help define whether the AE/CM started while taking study drug.

For a partial or missing start date:

- If the day is missing, the first day of the month will be imputed. If the missing day is the same as the month of first dose of study drug, then the first dose date will be imputed.
- If the day and month are missing, the first day of January will be imputed. If the year is the same as the first dose date, then the first dose date will be imputed.
- If the day is completely missing, the first dose date will be imputed. If the end date suggests it could have started prior to this, the first day of January of the same year as the end date will be imputed.
- When imputing a start date, the start date will ensure that the new imputed date is sensible, i.e., is prior to the end date of the AE or CM.

For a partial or missing end date:

- If the day is missing, the last day of the month or the last assessment date, whichever is earlier, will be imputed.
- If the day and month are missing, the 31st of December or the last assessment date, whichever is earlier, will be imputed
- If the date is completely missing, there will be a need to look at whether the AE/CM is still ongoing before imputing a date. If the ongoing flag is missing, then it will be assumed that AE is still present, or CM is still being taken (i.e., do not impute a date). If the AE/CM has stopped, then the last assessment date will be imputed.

These data imputations are for categorization purpose only and will not be used in the listings.

If the assessment of the relationship of the AE to KD025 is missing, then it will be assumed that the AE is related to KD025 and the AE considered as such in the frequency tables of possibly related AEs. No imputation should be done at the data level.

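### SAP start-date imputation has no open-label anchor, so a placebo crossover's incompletely dated adverse event that may have begun on KD025 can be counted under placebo

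*SAP*

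**What the plan says.** SAP 3.1.5 states a principle, "The assumption will be the worst or most conservative judgment when imputing AE and CM start and end dates", and a purpose, "The purpose of imputing a start date is to help define whether the AE/CM started while taking study drug". Its start-date rules are:

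- **Day missing:** "If the day is missing, the first day of the month will be imputed". The exception is the first-dose month: "If the missing day is the same as the month of first dose of study drug, then the first dose date will be imputed".
- **Day and month missing:** 1 January of the recorded year, except "If the year is the same as the first dose date, then the first dose date will be imputed".
- **Date wholly missing:** "If the day is completely missing, the first dose date will be imputed" (I read the word day here as date). The exception begins "If the end date suggests it could have started prior to this, the first day of January" and uses the year of the end date.
- **Check:** the imputed start must precede the end date.

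SAP 3.1.2 calls for safety tables for the blinded period, the open-label period and the entire duration. The blinded and entire-duration tables are by randomised cohort, with placebo as cohort 5. The open-label table is one KD025 400 mg QD group. SAP 3.9.1 adds: "TEAEs for open-label period are any AEs occurring or worsening in severity after Week 16". Protocol 9.2 lets subjects randomised to placebo take open-label KD025 from Week 16.

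**The concern.** The date rules know one reference point, the first blinded dose. The tables need two. SAP 3.1.4 does define a second baseline for the open-label period, but the date rules were not extended to match.

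The gap matters most for placebo subjects who cross to KD025. If such a subject has an event with an incomplete start date, and it may have begun on KD025, the rules can place it on or before Week 16. It then counts under placebo in the blinded table and is missing from the open-label KD025 table. The SAP resolves missing causality the other way, by treating the event as related to KD025. The percentage of subjects with adverse events in each group is the primary safety endpoint (Protocol 5.5 and 12.8).

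A second defect does not depend on period. The end-date exception for wholly missing dates has no operational test. Almost any end date after first dose is compatible with a start before it.

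**Working it through.** The plan gives no figure for this rule, so there is none to reproduce. I applied the rules as written.

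**Inputs**
- Week 16 is Day 112 and open-label treatment runs to Day 336 (Protocol Table 1-1). Open-label onset days are 113 to 336, so 336 − 112 = 224 days.
- Assumptions: onset uniform over those days; first-dose dates spread evenly over one calendar year (365 dates); end-date exception not triggered; blinded period ends at Week 16. SAP 3.9.1 states no end for blinded-period events, so the last is a reading.

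**Rule for booking.** Week 16 date = first-dose date + 111 days. An event is booked to the blinded period if its imputed start is on or before that date, because open-label events must occur after Week 16.

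**Share of true open-label onsets booked to the blinded period**

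| Known part of start date | Average | Range for mid-month first doses |
|---|---|---|
| None | 100% | 100% |
| Year only | 69.2% | 12% to 100% |
| Month and year | 6.6% | 10.7% to 12.1% |

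*Month and year.* Errors occur only in the calendar month of Week 16, where the 1st is never after Week 16. The average 6.6% is 0.066 × 224 = 14.8 days, about half a month. For a first dose on 15 March 2018, Week 16 is 4 July and 27 days of July remain: 27/224 = 12.1%.

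*Year only.* For a first dose on 15 August 2018, Week 16 is 4 December. The 27 onset days left in 2018 go to the first-dose date (27/224 = 12%), while 2019 onsets go to 1 January 2019, correctly after Week 16. For mid-month first doses from September to December, Week 16 falls in the next year, 1 January precedes it, and the share is 100%.

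*First-dose-month sentence.* The first-dose month equalled the Week 16 month in 0 of 365 × 3 = 1,095 combinations (Week 16 on Day 109, 112 or 115). That sentence shows the anchor but causes no misplacement.

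**Example.** First dose 10 January 2018, Week 16 on 1 May 2018.
- Onset 5 September 2018, recorded as 2018 only or not dated: imputed to 10 January 2018, blinded.
- Onset 20 May 2018, recorded as May 2018: imputed to 1 May 2018, the Week 16 date, so not after Week 16.
- Onset 5 September 2018, recorded as September 2018: imputed to 1 September 2018, correctly open-label.

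**One subject.** In a 22-subject placebo column, 1/22 = 4.5 percentage points, for any row in which that subject has no other qualifying blinded-period event.

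**1 January clause.** With the same first dose, take an event with no start date that ended on 20 June 2018. It could have started before 10 January, so the literal rule imputes 1 January 2018. That precedes treatment, and the event is no longer treatment-emergent in any arm. The effect needs an end date in the first-dose year. With a mid-June 2018 first dose and a March 2019 end date, the clause gives 1 January 2019, which is open-label.

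**The case against.** **The stated purpose is treatment emergence, not period.** For that purpose alone, anchoring on first dose is conservative. This stands, but the same dates also feed tables split at Week 16, and no other rule assigns the period.

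**Net bias against placebo is not shown.** A reader might infer that the KD025-versus-placebo difference must shrink. The documents do not support that. Subjects in cohorts 1 to 4 may also enter open-label treatment, and their incompletely dated events move into the blinded columns too. If such events are equally frequent across cohorts, the absolute difference hardly changes. For these subjects the event stays on KD025, though possibly at another dose.

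**Medications.** A reader might extend the point to concomitant medications. SAP 3.6 counts a medication in each period in which it is taken, so an early imputed start need not remove continuing open-label use. I make no claim there.

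**A blanket remedy would do harm.** Reassigning every compatible event to open-label would move true blinded onsets as well: 14.0% with the day missing, 84.8% with the year only and 100% with no date. Four of five cohorts (88 of 110 planned subjects) are randomised to KD025, so this would take possible KD025 events out of the only randomised placebo comparison. This stands and limits the fix.

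**Importance.** Onset dates must be recorded (Protocol 11.3.7), an event recorded as worsening after Week 16 still enters the open-label table, and entire-duration tables keep crossover events under cohort 5 whatever the imputation. The effect may be small.

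**Conclusion.** The point holds for placebo crossovers in the period-specific tables. As written, SAP 3.1.5 resolves an incomplete start date towards placebo when the event may have begun on KD025, contrary to its own principle. Under the stated assumptions the misplaced share of true open-label onsets is 100% with no date, about 69% with the year only and about 7% with only the day missing. These shares describe incompletely dated events only. Their number is not in the documents, so the absolute effect cannot be computed.

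It would be tempting to say that half of all month-only dates are misplaced. Under uniform dates that figure applies only within the Week 16 month; events dated to a later month are placed correctly.

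The 1 January clause is a separate defect. Read literally, it can strip treatment-emergent status from a wholly undated event that ended after first dose in the first-dose year. A programmer could read it more narrowly, but the SAP gives no test.

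**What to change.** Add two sentences to SAP 3.1.5.

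1. For subjects randomised to placebo who took open-label KD025, if the known parts of the start date and the end date allow an open-label onset, assign the adverse event to the open-label period for period tabulation. Subjects randomised to KD025 stay on the current rule. Show a sensitivity count under the alternative assignment.
2. Apply the 1 January rule only when the end date is before the first dose of study drug.

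The first is best done with a period flag. Imputing the first open-label dose date could fail, because that dose may fall on the Week 16 date and open-label events must come after Week 16.

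The cost is two sentences and a small change to the date-imputation program, with no new data. The downside is that some true placebo-period events will be booked to open-label KD025. Among incompletely dated ones, before the end-date condition removes any, the shares are the 14.0%, 84.8% and 100% given above. That is the conservative direction, and the sensitivity count shows how much depends on it.
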